**Study 270-301 Statistical Analysis Plan****7 DISCONTINUATION AND COMPLETION**

For treated subjects who prematurely discontinue study participation prior to the Week 52 visit, prior to the Week 104 visit or during long-term follow-up, the primary reason for discontinuation will be summarized. The number and percentage of subjects who are continuing the study, who completed Week 52, and who completed Week 104 will also be provided for all treated subjects.

**Study 270-301 Statistical Analysis Plan****8 PROTOCOL DEVIATIONS**

The trial's Study Specific Guideline for Managing Protocol Deviations defines protocol deviations, including whether they are minor or major. Major protocol deviations will be summarized. A data listing of protocol deviations will be provided as well.

9 DEMOGRAPHICS AND BASELINE CHARACTERISTICS

Subject demographic and baseline characteristics to be summarized include

- age at enrollment (year)
- age group (≥ 18 - < 65 , ≥ 65)
- age group (≥ 18 - < 30 , ≥ 30 - < 50 , ≥ 50)
- sex (Female/Male)
- ethnicity
- race
- height (cm)
- weight (kg)
- BMI (kg/m^2)
- baseline ECG evaluation
- history of liver disease (Yes/No)
- history of hepatitis B (Yes/No)
- history of hepatitis C (Yes/No)
- history of HIV (Yes/No)
- baseline disease characteristics including
 - time since diagnosis of hemophilia A (year)
 - type of FVIII treatment for hemophilia A (prophylaxis/episodic)
 - history of FVIII inhibitor (Yes/No)
 - FVIII genotyping results
 - number of target joints
 - body location of target joints
 - ambulatory assist device requirement (Yes/No)
- baseline FVIII activity (IU/dL) excluding values within 72 hours after a FVIII infusion

And for the following parameters, two sets of analyses will be performed to include data approximately 6-months (starting from Day 1 visit in study 270-902) or 12-months (starting from 6 months before Day 1 visit in study 270-902) prior to 270-301 study enrollment for study 270-902 rollover subjects, separately:

**Study 270-301 Statistical Analysis Plan**

- duration of baseline data collection periods, months
- baseline annualized utilization (IU/kg/year) of exogenous FVIII replacement therapy
- baseline annualized number of FVIII infusions (infusions/year)
- baseline ABR (treated bleeds/year)
- baseline ABR (all bleeds/year)

**Study 270-301 Statistical Analysis Plan****10 MEDICAL HISTORY**

Medical history will be coded using the most current version of Medical Dictionary for Regulatory Activities (MedDRA) at the time of coding. Medical history will be summarized by system organ class (SOC) and preferred term (PT).

11 PRIOR AND CONCOMITANT MEDICATIONS/PROCEDURES

Prior and concomitant medications are defined as follows:

- prior medication—any medication taken prior to the initiation of the investigational product and within 30 days prior to screening;
- concomitant medication—any medication taken after the initiation of the investigational product.

When a medication starts prior to the initiation of the investigational product and continues while on study, it will be summarized as both a prior and concomitant medication.

All medications will be coded using the current version of the World Health Organization Drug (WHO Drug) Dictionary.

Prior and concomitant medication use will be separately summarized by Anatomical Therapeutic Chemical (ATC) medication class (Level 4) and preferred name (i.e., generic medication name), and by NIH hepatotoxicity likelihood grades and preferred name as well. A subject reporting the same medication more than once will be counted once when calculating the number and percentage of subjects who received that medication.

Corticosteroid usage including total dose and total duration per subject, dose per corticosteroid course, duration per corticosteroid course, and time to corticosteroid course(s), and number of corticosteroid courses will be summarized for therapeutic purposes. Non-steroidal immunosuppressants may be summarized as well.

Baseline FVIII prophylaxis treatment will be summarized by type (extended half-life, standard half-life, and plasma derived) and drug preferred name.

Subjects who resume prophylactic treatment post BMN 270 infusion will be listed separately.

**Study 270-301 Statistical Analysis Plan****12 EXTENT OF EXPOSURE TO STUDY DRUG**

Each subject receive a single intravenous infusion of BMN 270, and the volume of infusion depended on the subject's weight. Actual dose (vg/kg), duration of infusion, initial and overall rate of infusion for each subject will be summarized descriptively. Investigational product dosing compliance will be assessed by providing descriptive summaries of actual dose, number and percentage of subjects with administered investigational product infusions below the planned dose, subjects with dose changes, and various reasons of dose changes. The post-BMN 270 follow-up time of each subject will be summarized descriptively.

A data listing of drug exposure will be provided.

13 EFFICACY EVALUATIONS

This section describes the analyses to be undertaken for the primary, secondary, and other efficacy variables as described in the protocol. Estimand formulation is provided for the primary endpoint.

Two interim analyses were planned when approximately 16 and 20 treated HIV-negative subjects have completed the Week 26 visit (or have discontinued study prior to Week 26), respectively. For controlling the probability of a type I error for the interim analyses, the 1-year analyses, and the 2-year final analyses of the primary efficacy endpoint, the fallback procedure was used. See Section 13.7 for additional information regarding the interim analyses and multiplicity adjustment.

13.1 Efficacy Evaluation Periods

To avoid breakthrough bleeding, subjects only discontinued exogenous prophylactic FVIII replacement therapy after 4 weeks following infusion of BMN 270. Four weeks represents the time by which endogenous production of FVIII following gene transfer is expected to be efficacious, based on earlier results. For the purpose of primary data analysis, the efficacy evaluation period for

- Efficacy endpoints such as ABR, number of treated bleeds, annualized FVIII utilization, annualized FVIII infusions and PROs: will be defined as starting from Week 5 post-BMN 270 dosing (Study Day 33) or 3 days after the end of FVIII prophylaxis, whichever is later, until subjects complete the study, reach the last visit by data cutoff for the analysis, or withdraw from the study (ETV), whichever is the earliest.
- Efficacy endpoint of FVIII activity based on chromogenic substrate assay: will be defined as starting from Week 5 post-BMN 270 dosing (Study Day 33) until subjects complete the study, reach the last visit by data cutoff for the analysis, withdraw from the study (ETV) (FVIII activities post withdrawal will be imputed to be 0 IU/dL through the data cutoff date for the analysis), or resume routine FVIII prophylaxis (should that occur) (Restart of FVIII prophylaxis is defined as the first usual FVIII prophylaxis administered at least once a week for ≥ 4 consecutive weeks), whichever is the earliest.

Study 270-301 Statistical Analysis Plan

- Efficacy endpoint of FVIII activity based on one-stage assay: will be defined as starting from Week 5 post-BMN 270 dosing (Study Day 33) until subjects complete the study, reach the last visit by data cutoff for the analysis, withdraw from the study (ETV) (FVIII activities post withdrawal will be imputed to be 0 IU/dL through the data cutoff date for the analysis), or resume routine FVIII prophylaxis or start emicizumab prophylaxis (should that occur) (Start of emicizumab prophylaxis is defined as the first emicizumab injection among 2 or more emicizumab injections administered within 31 days), whichever is the earliest.

For the purpose of supportive data analyses, the efficacy evaluation period for

- Efficacy endpoint of FVIII activity: will be defined as from BMN 270 infusion to until subjects complete the study, reach the last visit by data cut-off for the analysis, or withdraw from the study (ETV), whichever is the earliest.
- Efficacy endpoints such as ABR, number of treated bleeds, annualized FVIII utilization, annualized FVIII infusions: will be some of the efficacy evaluation periods listed in [Table 13.1.1](#). In addition, descriptive summary will be provided in Weeks 1-4 and Week 1-end of FVIII prophylaxis (defined as end of week 4 post-BMN 270 infusion or 2 days after end of FVIII prophylaxis, whichever is later).

Time to discontinuation of FVIII prophylaxis post-BMN 270 infusion and duration of efficacy evaluation period for primary analysis of primary and secondary efficacy endpoints will be summarized.

[figure not shown]

Table 13.1.1: Efficacy Evaluation Periods for Analyses of Primary and Second-Ranked Secondary Efficacy Endpoints

Efficacy Evaluation Period	Start Point	End Point	Analysis
Post-FVIII prophylaxis period	Start of Week 5 post-BMN 270 infusion or 3 days after end of FVIII prophylaxis, whichever is later	Last visit by data cut-off	Primary, t-test
Post-FVIII prophylaxis – week 104	Start of Week 5 post-BMN 270 infusion or 3 days after end of FVIII prophylaxis, whichever is later	Last visit by data cut-off or end of Week 104 post-BMN 270 infusion, whichever is earlier	Supportive, t-test
Post-FVIII prophylaxis – restart of prophylactic treatment up to Week 104	Start of Week 5 post-BMN 270 infusion or 3 days after end of FVIII prophylaxis, whichever is later	Last visit by data cut-off, end of Week 104 post-BMN 270 infusion or 1 day before restart of prophylactic treatment, whichever is earlier	Supportive, t-test
Post-FVIII prophylaxis – restart of prophylactic treatment up to last visit	Start of Week 5 post-BMN 270 infusion or 3 days after end of FVIII prophylaxis, whichever is later	Last visit by data cut-off or 1 day before restart of prophylactic treatment, whichever is earlier	Supportive, t-test

Note: end of FVIII prophylaxis is defined as last usual FVIII prophylaxis not followed by another usual FVIII prophylaxis for at least 28 days.

Restart of prophylactic treatment means restart of FVIII or start emicizumab prophylaxis. Restart of FVIII prophylaxis is defined as the first usual FVIII prophylaxis administered at least once a week for ≥ 4 consecutive weeks. Start of emicizumab prophylaxis is defined as the first emicizumab injection among 2 or more emicizumab injections administered within 31 days.

Study 270-301 Statistical Analysis Plan

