13.3 Secondary Efficacy Endpoints

The first-ranked secondary efficacy endpoint is:

- The change from baseline (assuming no treatment for severe hemophilia A) in FVIII activity, as measured by chromogenic substrate assay, at Weeks 104 post-BMN 270 infusion

Each subject's FVIII activity level at Week 104 is defined as the median of the values obtained at Week 104 with the window defined in Appendix 20.1. The baseline value will be imputed as 1 IU/dL, since there will be no washout of severe hemophilia A subjects' usual FVIII prophylaxis (in order to avoid increasing the risk of bleeding) prior to BMN 270 infusion. Post-BMN 270 infusion values for FVIII activity will be excluded from analysis if obtained within 72 hours (or 3 calendar days if time is not available) since the last infusion of exogenous FVIII replacement therapy.

The second-ranked secondary efficacy endpoint is:

- The change from baseline (prior to BMN 270 infusion while receiving FVIII prophylaxis) in the annualized utilization (IU/kg/year) of exogenous FVIII replacement therapy in the efficacy evaluation period ("Post FVIII Prophylaxis to Last Visit")

The annualized utilization (IU/kg/year) of exogenous FVIII replacement therapy is defined as

$$\frac{\text{Sum of FVIII use (IU/kg) during calculation period}}{\text{Total number of days during the calculation period}} \times 365.25$$

The primary analyses for the annualized utilization (IU/kg/year) of exogenous FVIII replacement therapy will be performed on the Study 270-902 rollover subjects.

The calculation period in these formulas for the post-baseline value is:

- For the primary analysis, the efficacy evaluation period ("Post FVIII Prophylaxis to Last Visit") as defined in Section 13.1.
- For the supportive analyses, the efficacy periods as defined in Section 13.1.

The calculation period for the baseline value is defined in the following:

- For the primary analysis, the calculation period is approximately 6 months in the non-interventional study 270-902; i.e., the baseline values will be derived from the prospectively collected 6-month data in 270-902 up until the BMN 270 infusion date in 270-301.

Study 270-301 Statistical Analysis Plan

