13.3.2 Supportive Analysis Methods for Secondary Efficacy Endpoints

The FVIII activity level will be summarized descriptively in 4 or 6-week visit windows with missing data imputed from baseline up to the last possible visit by the data cut-off for the 2-year analysis (eg. if a subject was lost to follow-up at Week 60 and would have been followed for 104 weeks by the data cut-off, his FVIII activity levels beyond Week 60 will be imputed to be 0 IU/dL up to Week 104). The visits and visit windows are defined in Appendix 20.1 Visit Windows. Each subject's FVIII activity level in a visit window is defined as the median of the values obtained during the window. The number and proportion of subjects achieving FVIII activity level per chromogenic assay of <LLoQ (3 IU/dL), between levels of \geq LLoQ (3 IU/dL)-<5 IU/dL, between the levels of \geq 5-<15 IU/dL, between the levels of \geq 15-<40 IU/dL, between the levels of \geq 40-<=150 IU/dL, and >150 IU/dL will also be summarized every 4 or 6 weeks from baseline up to data cut-off. The number and proportion of subjects whose FVIII activity is <5, \geq 5-<40 and \geq 40 IU/dL will also be provided.

Boxplots of median FVIII activity values using chromogenic substrate assay at 4-week or 6-week windows (Appendix 20.1 Visit Windows) over time will be provided.

The by 4 or 6-week analysis will be repeated using efficacy evaluation period for supportive analysis of FVIII activity without imputation for mITT population.

The maximum of each subject's FVIII activity levels (medians of the values in visit windows defined in Appendix 20.1), and the time to the maximum level, will be summarized descriptively. The number and proportion of subjects whose maximum FVIII activity level is < LLoQ (3 IU/dL), between levels of \geq LLoQ (3 IU/dL)-<5 IU/dL, between the levels of \geq 5-<15 IU/dL, between the levels of \geq 15-<40 IU/dL, between the levels of \geq 40-<=150 IU/dL, and >150 IU/dL will also be summarized.

The primary and supportive analyses described above may be conducted for FVIII activity values by one-stage clotting assay.

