**Study 270-301 Statistical Analysis Plan**

To investigate the relationship between the FVIII activity values by one-stage clotting and chromogenic substrate assays, a linear regression to fit a line to the observed values by these two assays will be conducted for the mITT population.

For long-term FVIII activity data, the overall trend will be examined. The FVIII activity levels, their changes from baseline, will be summarized descriptively at milestone timepoints defined as the end of every 6 months post-BMN 270 infusion (eg, Weeks 23-26, Weeks 49-52, Week 76 and 104 with the visit windows defined in Appendix 20.1). Missing data will be imputed using the imputation methods specified in Section 5.6. In addition, proportion of subjects whose FVIII level is < LLoQ (3 IU/dL), between levels of \geq LLoQ (3 IU/dL) - < 5 IU/dL, between the levels of \geq 5 - < 15 IU/dL, between the levels of \geq 15 - < 40 IU/dL, between the levels of \geq 40 - \leq 150 IU/dL, and > 150 IU/dL will be summarized. The change in FVIII activity between certain milestone timepoints (eg, between Weeks 23-26 and Weeks 49-52, between Weeks 49-52 and Week 76, between Week 76 and Week 104) and between Week 104 and the maximal FVIII activity by the Week 104 will also be summarized. In addition, LOESS (locally estimated scatterplot smoothing) curves of FVIII activity will be generated to show the overall trend, to compare trends between directly enrolled subjects and Study 270-902 rollover subjects, and to compare trends observed in Study 270-301 with those observed in 4E13 and 6E13 vg/kg cohorts of the Phase 2 Study 270-201.

Exploratory analyses including univariate and multiple logistic regression may be performed to evaluate associations between demographic and baseline characteristics and other parameters and FVIII activity at Week 104 to assess potential predictors of variability.

Total and annualized FVIII utilization (IU/kg/year) will be listed by subject and by periods (pre-BMN 270 infusion [baseline period], Weeks 1-4, Week 1 to end of original FVIII prophylaxis, Post FVIII Prophylaxis-52, Weeks 53-104, and the efficacy evaluation periods as defined in Table 13.1.1), and the annualized utilization rates will be summarized descriptively.

The analysis for the change from baseline in the annualized utilization (IU/kg/year) of exogenous FVIII replacement therapy will be conducted using data in the efficacy evaluation periods as defined in Table 13.1.1.

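### One-stage FVIII values after emicizumab start are cut off in the primary period but not in the supportive period, the assay regression or the one-stage bleeding regression

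*SAP*

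**What the plan says.** SAP Section 13.1 sets the FVIII-activity periods for the primary analysis by assay. The chromogenic period starts at Week 5 (Study Day 33) and ends at study completion, last visit by cut-off or withdrawal, "or resume routine FVIII prophylaxis (should that occur) (Restart of FVIII prophylaxis is defined as" the first of a run of usual prophylaxis. The one-stage period has the same start and the same stops, plus one more: "or resume routine FVIII prophylaxis or start emicizumab prophylaxis (should that occur". The same section defines emicizumab start as the first of two or more injections within 31 days.

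For supportive analyses, Section 13.1 gives one definition and names no assay: "Efficacy endpoint of FVIII activity: will be defined as from BMN 270 infusion to until subjects complete the study", reach the last visit by cut-off, or withdraw. It contains neither the FVIII-restart stop nor the emicizumab stop.

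Section 13.3 removes post-infusion FVIII-activity values "if obtained within 72 hours (or 3 calendar days if time is not available) since the last infusion of exogenous FVIII replacement therapy". The SAP has no similar rule for emicizumab.

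Three analyses use one-stage values without a stated emicizumab limit:

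- Section 13.3.2, supportive summaries: "The by 4 or 6-week analysis will be repeated using efficacy evaluation period for supportive analysis of FVIII activity without imputation for mITT population". The one-stage version is optional: "The primary and supportive analyses described above may be conducted for FVIII activity values by one-stage clotting assay".
- Section 13.3.2, relation between the assays: "a linear regression to fit a line to the observed values by these two assays will be conducted for the mITT population". This is a firm commitment, and no evaluation period is named.
- Section 13.3.4, negative binomial regression of bleeds per window on FVIII activity in that window. It is to be run separately for each assay. This is also firm, and again no period or emicizumab exclusion is given.

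**The concern.** The two primary periods differ only in the emicizumab stop. If that stop merely marked a change of treatment, it would apply to both assays. Applying it to the one-stage assay alone suggests that the sponsor does not want one-stage readings on emicizumab counted as transgene activity. The plan then leaves such readings available in other analyses.

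The subjects concerned are not a random subset. Section 13.3.5 foresees emicizumab for subjects with recurrent bleeding, so they would tend to be poor responders with low chromogenic values. If emicizumab alters a one-stage value, the pair falls at the low end of the chromogenic axis of the assay regression, where a misplaced point shifts the intercept. In the bleeding regression, emicizumab could affect both variables at once: the one-stage reading, and the number of bleeds through its own prophylactic effect. In the optional summaries, a subject who has lost response could be placed in too high an activity category.

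**Working it through.** The SAP gives no figure for this point to reproduce. The check compares the rules that decide which one-stage values are used.

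**Step 1. Stops by period (Section 13.1)**

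| Period | Starts | Stops at FVIII restart | Stops at emicizumab start |
|---|---|---|---|
| Primary, chromogenic | Day 33 | yes | no |
| Primary, one-stage | Day 33 | yes | yes |
| Supportive, no assay named | infusion | no | no |

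**Step 2. Is there another filter?** The 72-hour rule in Section 13.3 still screens samples taken soon after exogenous FVIII, so dropping the FVIII-restart stop does not leave those samples unscreened. Emicizumab has no matching rule. Dropping its stop leaves nothing.

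**Step 3. Where can the values enter?**

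| Analysis | Commitment | Period stated | Emicizumab limit |
|---|---|---|---|
| Assay regression, 13.3.2 | firm | none | none |
| One-stage bleeding regression, 13.3.4 | firm | none (visit windows only) | none |
| By-window repeat without imputation, one-stage version, 13.3.2 | optional | supportive | none |

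The other by-window and milestone summaries in 13.3.2 are not assigned to the supportive period by name. If run for the one-stage assay, they could follow the one-stage primary period, which does stop at emicizumab. They are therefore not counted here.

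**Step 4. Size.** The SAP gives neither the number of emicizumab starters nor the number of later one-stage readings, so the actual effect cannot be computed. It is nil with no starters.

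An illustration on assumed data shows how far the answer depends on the inputs. The number of subjects follows from the SAP: 134 treated − 2 HIV-positive = 132 in the mITT population. Everything else is assumed: lognormal chromogenic values with median 15 IU/dL and log-SD 1.0, one-stage = 1.6 × chromogenic with 10% noise, and the lowest 1 to 3 responders given a fixed one-stage reading on emicizumab.

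| Design | Assumed reading | R² (1 to 3 subjects) | Intercept, IU/dL |
|---|---|---|---|
| One pair per subject, none affected | – | 0.986 | about 0 |
| One pair per subject | 50 IU/dL | about 0.98 to 0.96 | 0.6 to 1.8 |
| One pair per subject | 100 IU/dL | 0.95 to 0.89 | 1.3 to 3.8 |
| One pair per subject | 200 IU/dL | 0.86 to 0.67 | 2.7 to 7.7 |
| 27 pairs per subject, none affected | – | 0.984 | about 0 |
| 27 pairs per subject, last 7 affected | 100 IU/dL | 0.977 to 0.963 | 0.3 to 0.9 |
| 27 pairs per subject, last 7 affected | 200 IU/dL | 0.954 to 0.904 | 0.7 to 2.0 |

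At an assumed reading of 20 IU/dL the effect is trivial. At 100 IU/dL the slope hardly moves: 1.60 to about 1.54 with three subjects and one pair each, and about 1.60 with 27 pairs. The design with many pairs is closer to a fit of all observed values over two years, and there the effect is small unless the assumed reading is high.

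**The case against.** The strongest reply is that the supportive period is broad on purpose. It starts at infusion instead of Week 5, drops the FVIII-restart stop for both assays as well as the emicizumab stop, and is used without imputation. That reads as a view of all observed data set beside the restricted primary period. This is a fair account of the period, but it does not close the gap: in that broad view samples close to exogenous FVIII are still removed by the 72-hour rule, while one-stage samples on emicizumab are not removed by any rule.

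It is also fair that the one-stage summaries are optional, and that the assay regression names no period and so cannot be said to run on the supportive one. That leaves its data set open. It does not keep the values out.

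Three stronger readings are tempting, and the SAP does not support them:

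- A reader might infer that the plan declares these readings invalid. It does not: it gives no reason for the stop. The inference rests only on the stop being specific to one assay.
- A reader might infer that the fitted relation is used to carry results from one assay to the other. No section does so. Section 13.3.2 only investigates the relationship.
- A reader might infer a serious loss of fit in the regression. The lowest R² values above need high assumed readings and a single pair per subject, and neither comes from the SAP.

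**Conclusion.** The inconsistency is real and minor. The plan cuts off one-stage values at emicizumab start in one place. As written, it lets them into two firm regressions and one optional set of summaries.

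The effect is confined to supportive and exploratory results. The tested FVIII endpoint is chromogenic, one-stage activity is not among the nine hypotheses in Section 13.7, and the tests of ABR, FVIII utilization and Haemo-QoL-A do not use it. The size is unknown and is nil if no subject started emicizumab. The conclusion rests on one inference, that a stop applied to the one-stage assay alone reflects doubt about one-stage readings on emicizumab. It does not depend on the illustrative figures.

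**What to change.** In Section 13.1, split the supportive FVIII-activity period by assay and, for the one-stage assay, end it at the start of emicizumab prophylaxis as that section already defines it. In Section 13.3.2, state which data the assay regression uses and exclude one-stage values from emicizumab start onward. Apply the same exclusion to the one-stage regression in Section 13.3.4. If the sponsor also wants an all-data view, it can be kept as a labelled extra with the affected readings marked.

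The cost is a few sentences and one filter on data already collected. The downside is the loss of a few one-stage values. The chromogenic analyses do not change.
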